Study protocol: Development of a Tobacco Control Trial among Migrant Workers in Guangzhou, China

Background

It has been widely accepted that cigarette smoking is of tremendous hazards to health, so as the exposure to Secondhand Smoke (SHS). Cigarette smoking increases the incidence of maternal cardiovascular and pulmonary events and other comorbid conditions among pregnant smokers¹. Women make up 80% of the total disease burden of SHS². Kinds of respiratory symptoms were more frequently observed among adults exposed to SHS^{3,4}.

China signed WHO Framework Convention on Tobacco Control (FCTC) in 2003. However, there is still a significant gap between the current state of tobacco control and the requirements of the FCTC, mainly due to the state tobacco monopoly in China¹³.

As reported by the Global Adult Tobacco Survey (GATS)⁶, in 2010, an estimated 28.1% of adults in China (52.9% of men and 2.4% of women) currently smoked. As reported by nonsmokers, 72.4% had been exposed to secondhand smoke and 38.0% were exposed to secondhand smoke on a daily basis⁷. The direct medical cost of smoking-related morbidity and mortality was estimated at 22.9 billion Chinese Yuan⁵, and keeps increasing at a staggering rate.

In China, internal rural-to-urban migrants make a large proportion of the whole population, accounting for about 0.245 billion (18 % of the total population) in 2013. The national data of smoking in migrant population is still lacking. Studies shows that in Beijing, the total smoking rate of migrant population was 19.2% (48.7% for male and 2.1% for female)⁸ and in another study was 51.7% (male) and 10.9% (females)⁹. One study in Zhejiang province found that 29.83% of 1086 migrant population have smoked, 54.09% of whom were males¹⁰. A survey of five areas of Jiangxi province shown the total smoking rate was 32.8% (56.3% for male and 2.5% for female)¹¹. Cui et al found the overall smoking prevalence among migrant workers was 64.9% (95% CI: 62.4-67.2%)¹². These researches shown that the smoking rate was generally higher in migrant population than local residents.

Interventions targeting at migrant population on reducing smoking, including workplace interventions are still scarce. Zhong¹⁵, applied knowledge education to in workplaces, with smoking rate reduced from 42.9% to 28.9%. Gao¹⁶, used a health promotion strategy in a factory of Shanghai, making the smoking rate decreased from 55.8% to 34.1%.

Tobacco control intervention for migrant population often involved the general factors like hazard awareness¹⁷, diseases prevention, family pressure and financial pressure¹⁸. Research also shown that migratory lifestyle, such as social changes and stresses caused by rural to urban migration, was associated with smoking initiation¹⁹. The migrant span, migrant history, discrimination and social support all contribute to smoking²⁰⁻²³. However, it is unknown to what extent the comprehensive intervention that considers these factors can be effective in

reducing the smoking rate and SHS exposure for the migrants in the workplace settings in China.

Research questions

1. How can the WHO 5A's model be adapted into 5A's group consulting intervention package that fits migrant workers in China?
2. To what extent it is feasible and acceptable of delivering the intervention in the workplaces setting, and how the evidence generated from this study will inform the design of the main trial.

Methods/Design

This is a controlled before and after designed pilot trial to be conducted in manufacturing factories in Zhongshan City, China.

Study design

First, the package would be designed by tailoring the WHO 5A's model into 5A's group consulting intervention package through literature review, in-depth interview and focus group discussion. Then a pilot trial of the package will be carried out in 4 factories in Zhongshan industrial zone. The primary outcome of this pilot trial will be the feasibility and acceptability

of delivering the intervention and feasibility of assessing its outcomes. The secondary outcome includes information to inform the design of the future RCT, such as sample size, and facilitators and barriers of implementation in industrial settings.

Objective 1

To tailor the WHO 5A's model into 5A's group consulting intervention package that fits migrant workers.

Key activities

Based on literature review on articles related to migrant workers' smoking and SHS exposure, as well as the WHO 5A's model, we will conduct in-depth interview and focus group discussion to understand: 1) Which specific factors affecting migrant workers' smoking cessation should be considered in the intervention. 2) In which way the group consulting intervention should be applied in the industrial setting. 3) What specific content should be contained in the group consulting package to make the package effective?

Settings & Participants

In-depth interviews will be conducted with 4-6 factory managers and 6-8 migrant workers. Four focus groups with 6-8 factory managers/workers/health educators in each group will be conducted in factories.

Data collection

Facilitator guided discussions (FDG) will be conducted by the research team. The FDG guideline will be constructed with the help of factory managers/workers/health educators, and will be pilot tested with two in-depth interviews and a focus group. All the FDGs will be

recorded.

Objective 2

To test the feasibility and acceptability of delivering the intervention, and provide information to the design of the main trial such as outcome suitability, number of clusters (factories) and size of each cluster (participants), effect size, intra-cluster correlation coefficient (ICC) , recruitment and attrition rates.

Key activities

We aim to recruit 8 factories (clusters) and all the migrant workers working in these factories from industrial zone of Guangzhou, China. The clusters will be randomized to the intervention and control group in a 1:1 ratio. Clusters allocated to the intervention arm will be offered the 5A's group consulting package. The clusters in the control arm will not be offered the package until the completion of the study. All the migrant workers who work in each factory and provide informed consent will be recruited. Factories will complete a factory survey of basic factory information, all participants will complete a questionnaire (about the status of tobacco exposure, knowledge and attitude of tobacco, and demographic information), and a non-smoking individual will provide a saliva sample which will be tested for cotinine. All these participant outcomes (questionnaire and saliva cotinine) will be measured before and after the 3-month intervention in both arms of the trial. In addition, a purposive sample of participants will be invited for interviews to investigate the facilitators and barriers for integrating 5A's group consulting package into workplace settings and how these can be enhanced or addressed at the end of this trial.

The 5A's group consulting package intervention includes:

1. Factsheets detailing key information on smoking, SHS.
2. Guidelines for group guiders on how to deliver the 5A's group consulting (activities for different audiences: smokers, non-smokers exposed to SHS).
3. A leaflet that contains the key facts about smoking and SHS that can be disseminated to migrant workers after consulting.

Eligibility criteria

Inclusion criteria for cluster recruitment: 1. Factory should be labor intensive in manufacture industry. 2. Have at least 80 migrant workers that can participate in the trial. 3. The manager should be willing to adhere to the planed intervention. Exclusion criteria: 1. Have taken part in a similar tobacco control activity before.

We plan to recruit all the migrant workers working in each factory. We will include rural to urban migrants, no matter whether they smoke or not, who are willing to participate in the trial. We will exclude workers who do not smoke and have no SHS exposure at all.

Data collection

For objective 2, we have mainly outcomes as follows:

Category	Variables	Methods	Population targeted	Outcomes
Primary outcome	Feasibility	Questionnaire in intervention group and in-depth interview	Intervention deliver, migrant workers and factory manager	1.Satisfaction rate 2.Feasibility score
	Acceptability	Questionnaire in	Intervention deliver,	1.Satisfaction rate

		intervention group and in-depth interview	migrant workers and factory manager	2.Intent to use rate
Secondary outcome	Salivary cotinine	Salivary cotinine test conducted before and after the intervention	Non-smoking migrant workers	1.Salivary cotinine concentration
	Smoking status	Questionnaire survey conducted before and after the intervention	Smoking migrant workers	1.Smoking quit rate
	Knowledge, attitude	Questionnaire survey conducted before and after the intervention	Migrant workers	1.Knowledge change 2.Attitude change
	Attrition rate, intraclass correlation coefficient(ICC)	The whole research progress	Migrant workers	1.Attrition rate 2.ICC

For each factory in the study the following information will be recorded at the start of the study: Factory scale, types of factory products, demographic composition.

At baseline, each migrant participant will complete a questionnaire encompasses four main dimensions: (1) demographic characters; (2) migrant characters; (3) smoking behaviors and practices; (4) smoking related knowledge and attitudes. The same dimensions will be covered in the follow up survey three months after the baseline survey.

Cotinine is a metabolite of nicotine, and can be most sensitively and specifically measured by salivary cotinine samples, which have a half-life period of 12 to 18 hours and thus can reflect the degree of tobacco exposure^{25,26}. We will thus collect a saliva sample to measure salivary cotinine levels at baseline and a second saliva sample from the same participants three months after intervention start.

We will conduct in-depth interviews with twenty participants, five package deliverers and five factory managers at baseline, and at program completion (3 months post baseline). All the interview contents will be recorded.

Intervention fidelity

To maintain the quality of the intervention delivery and track fidelity to the intervention, we will use the following approaches. Firstly, the team leaders will be asked to submit an implementation form every week to research team to report the adherence to protocol, barriers to the implementation of the intervention and their suggestions. PI, Co-PI and research team of this project will look over these forms and provide feedback to all the team leaders to help them to conduct the interventions better. Secondly, migrant workers will also self-report the adherence to the intervention, the barrier to quit smoking and the satisfaction to the team leaders' work by instant messaging to the research team directly. In addition, at the end of each month, the research team will go to the intervention factories to talk with the team leaders about intervention progress and offer some professional resolutions. As for those

unqualified team leaders, they will be re-trained or replaced.

Data management

Data will be collected at baseline, and at program completion (3 months post baseline).

To avoid missing and logic mistakes in the questionnaires, all completed questionnaires will be checked by the interviewers when submitted, and the unqualified items in the questionnaires will be asked to modify by the migrant workers. All participants will provide at least 2mL saliva samples for salivary cotinine concentrate test. We will require all participants to refrain from eating, drinking, or smoking at least one hour before sample collection. We will collect salivary samples on the day of transport, and samples will be labeled and stored in EP tubes (Eppendorf Tubes) at -20°C until laboratory analysis. Samples will be analyzed using liquid chromatography-tandem mass spectrometry (LC/MS/MS) method. All experiments will be duplicated. The laboratory technicians will be blinded to participants' smoking status.

For those are lost to follow-up, the reasons of dropping out will be recorded. Before data can be analyzed, it will be processed, including correcting data-inputting errors by using double data entry method and range and logic checks. All personal information about the enrolled participants will not be shared with any third party during and after the trial to protect confidentiality. Questionnaires will be well stored in a locked room. Saliva will be destroyed after detection. Data will be stored in a secure database with password encrypted.

Data analysis

Data from baseline and follow-up will be analyzed using descriptive statistics (means, standard deviations, frequencies, etc.). The level of significance will be set at 0.05. IBM SPSS 20.0 and STATA 12 will be employed for analysis. Data will be analyzed to evaluate program fidelity, adaptations, effectiveness, factors that facilitated and challenged program delivery, and recommendations for improvement. Analyses will follow the intention-to-treat (ITT) principle; multiple imputation chained equation (MICE) method will be used to address missing or incomplete data. Difference-in-difference (D-in-D) analyses will be used to evaluate the effectiveness of the intervention. Logistic regressions and multiple linear regressions will be respectively employed to explore factors associated with the change of the outcome variables over time in the intervention arm, and results were represented as odds ratios (OR) with 95% confidence intervals (95% CI).

Acknowledgements

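### The protocol takes saliva from non-smokers only in two places and from all participants in a third, and under either reading the quit rate is unverified self-report

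*Protocol*

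**What the plan says.** The Protocol describes the saliva sample in three places.

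- **Objective 2, Key activities:** "a non-smoking individual will provide a saliva sample which will be tested for cotinine".
- **Data collection, outcome table:** the salivary cotinine row gives its target population as "Non-smoking migrant workers".
- **Data management:** "All participants will provide at least 2mL saliva samples for salivary cotinine concentrate test". The next sentence adds: "We will require all participants to refrain from eating, drinking, or smoking at least one hour before sample collection". On the assay, the section says "The laboratory technicians will be blinded to" smoking status.

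Eligibility criteria admits both groups: "We will include rural to urban migrants, no matter whether they smoke or not, who are willing to participate in the trial".

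In the outcome table the smoking-status row applies to smoking workers. Its outcome is "1.Smoking quit rate" and its method is "Questionnaire survey conducted before and after the intervention". No section uses cotinine, a cut-off or any other test to confirm quitting or claimed non-smoking. Data collection gives the purpose of cotinine as showing how much tobacco exposure a person has had, quotes a half-life of 12 to 18 hours, and says the second sample comes from the same people as the first.

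**The concern.** There are two linked problems. First, the sampled population is contradictory, and this has to be settled before the baseline visit. An analysis plan written later cannot supply a specimen that was never taken.

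Second, the quit rate depends on what workers say about themselves after one arm has had three months of group cessation counselling and the other has had nothing. If workers in intervention factories over-claim quitting more than control workers do, the difference between arms is biased in favour of the package. Objective 2 says that the pilot will supply the main trial with an effect size and a judgement on outcome suitability, and Data analysis evaluates effectiveness by difference-in-difference. A biased quit rate would therefore carry forward into the design of the main trial.

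**Working it through.** The Protocol gives no quit rate, misreporting rate or cotinine level, so there is no stated figure to reproduce. The check is mainly a comparison of the text, with one illustration on assumed rates.

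**Step 1: can the three statements be reconciled?** Reading the Data management wording as shorthand for all *sampled* participants does not fit well. A no-smoking instruction, and keeping technicians unaware of smoking status, both point to a sample that includes smokers. The other two places say non-smokers explicitly. Since smokers are enrolled, the populations differ.

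**Step 2: can quitting be verified under either reading?**

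- *Non-smokers only:* the second sample is from the same people as the first, so a baseline smoker who reports quitting is never sampled. Verification is impossible.
- *All participants:* the needed samples exist, but the Protocol gives them no such use.

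Either way the quit rate rests on the questionnaire alone.

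**Step 3: illustration of the bias.** Assume true quitting of 5% in both arms, with a fraction q of continuing smokers claiming to have quit. The observed rate is 0.05 + 0.95 × q. The true odds are 0.05/0.95 = 0.0526.

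| q, intervention | Observed rate | Odds | OR, control q = 0 | OR, control q = 2% |
|---|---|---|---|---|
| 2% | 6.90% | 0.0741 | 1.41 | 1.00 |
| 5% | 9.75% | 0.1080 | 2.05 | 1.46 |
| 10% | 14.50% | 0.1696 | 3.22 | 2.29 |

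With 10% against 5% over-claiming, the OR is 0.1696/0.1080 = 1.57. With equal over-claiming it is 1. The true OR is 1 throughout. If quitting is counted among baseline smokers, it is zero at baseline by definition. The difference-in-difference is then just the follow-up difference and removes none of this.

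**Step 4: smokers among claimed non-smokers.** Let M be the amount that misclassified smokers add to an arm's mean cotinine at one time point. Their contribution to the difference-in-difference is (M at follow-up − M at baseline) in the intervention arm, minus the same quantity in control. The same people are sampled twice, so stable misclassification largely cancels, even if the arms start at different levels. What remains is extra variance, and bias only if the misclassification changes differently by arm.

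**Step 5: what a cotinine check can show.** At a half-life of 12 to 18 hours, 72 hours without tobacco is 72/18 = 4 to 72/12 = 6 half-lives. That leaves 1/16 to 1/64 of the starting level (6.3% to 1.6%). A negative test therefore supports recent abstinence only.

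**The case against.** The best defence is proportion. This is a feasibility pilot. The outcome table measures feasibility and acceptability by satisfaction, a feasibility score and intent to use, none of which depends on saliva or the quit rate. Biochemical verification is a reasonable refinement rather than a precondition, and an unverified quit rate is tolerable if labelled as such. The cut-off value may properly sit in an analysis plan that is not shown. The rates in the illustration are assumed, and the largest odds ratios need no over-claiming at all in control factories. All of this stands, and it limits the weight of the point. It does not remove the contradiction over who is sampled, or the questionnaire-only method, both of which the Protocol itself fixes.

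Some stronger readings are tempting but unsupported:

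- *Workers report quitting to team leaders, or to interviewers who know the arm.* The Protocol does not say so. Participants complete a questionnaire, and interviewers check it for gaps and logic errors. The messages described under Intervention fidelity go directly to the research team and cover adherence, barriers and satisfaction. That workers can infer their arm is itself an inference from the delayed-package control.
- *A few misclassified smokers would overwhelm the cotinine comparison.* Step 4 shows that they mainly add noise to a change-from-baseline contrast.
- *Technicians unaware of smoking status but not of arm are a material source of bias.* For a duplicate LC/MS/MS assay this matters little.

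**Conclusion.** The point holds. The saliva population is stated inconsistently and must be reconciled before sampling. Under either version the quit rate is unverified self-report and open to bias if over-claiming differs by arm. On the stated assumptions (5% true quitting in both arms, 2% to 10% over-claiming in intervention factories, none in control), the spurious odds ratio runs from 1.4 to 3.2. It shrinks towards 1 as control over-claiming approaches the intervention level. These figures show what is possible; they do not estimate what will happen.

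The consequence is confined to a secondary outcome and to the effect size handed to the main trial. A reader might infer that the pilot's primary outcomes are undermined, or that the all-participants wording is the intended one. The documents support neither: the primary measures do not use these data, and two of the three places say the opposite.

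**What to change.** State one saliva population, in the same words, in Objective 2 (Key activities), the outcome table and Data management. The sponsor must say which was intended. Then:

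- **If all participants are sampled:** define a quit as self-report plus follow-up cotinine below a cut-off fixed in advance. Apply that cut-off to claimed non-smokers at baseline in the secondhand-smoke analysis. State that a negative result confirms only recent abstinence. On this reading the samples are already planned, so the cost is wording, and the quit rate will be somewhat lower.
- **If only non-smokers are sampled:** correct Data management, including the sentences that presuppose smokers in the sample. Report the quit rate as unverified self-report, and do not pass it to the main trial as an unbiased effect size. The cost is wording and a weaker claim.

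### Whole factories are allocated, but the 0.05-level effectiveness analysis names no allowance for factory clustering, so its type I error exceeds 5% if factory is ignored

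*Protocol*

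**What the plan says.** The unit of allocation is the factory. Under Objective 2, Key activities, the protocol says "The clusters will be randomized to the intervention and control group in a 1:1 ratio". The Study design text uses a different label ("This is a controlled before and after designed pilot trial"), but under either description whole factories receive or do not receive the package.

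The number of factories is given twice and differently. Objective 2 says "We aim to recruit 8 factories (clusters"; Study design says "Then a pilot trial of the package will be carried out in 4 factories in Zhongshan industrial zone". The Eligibility criteria set a minimum size for each factory: "Have at least 80 migrant workers that can participate in the trial".

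The Data analysis section then fixes three things that matter here:

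- the level: "The level of significance will be set at 0.05";
- the effectiveness method: "Difference-in-difference (D-in-D) analyses will be used to evaluate the effectiveness of the intervention";
- the regression families: "Logistic regressions and multiple linear regressions will be respectively employed", for exploring what is associated with change within the intervention arm.

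The ICC appears under Objective 2 as information for the main trial, and in the outcome table as a secondary outcome. No sentence carries it, or any other account of factory, into a standard error, test or degrees of freedom of this trial.

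**The concern.** Workers in one factory share managers, workplace smoking rules, team leaders and, in the intervention arm, the counselling groups themselves. Their changes over three months are therefore likely to be positively correlated. The independent replicates for the comparison of arms are the factories, of which there are 8 or 4, and not the several hundred workers.

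An analysis that leaves factory out gives intervals that are too narrow and p-values that are too small for any positive correlation. It could present ordinary variation between factories as an effect of the package. The outcomes at risk are salivary cotinine, quit rate, knowledge and attitude. The protocol also wants an effect size from this pilot for the design of the main trial, and a spuriously precise estimate would mislead that step.

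**Working it through.** There is no sample size, power figure or ICC in the protocol to reproduce. The only stated figure is the level of 0.05 (two-sided assumed), so the check is whether that level would hold.

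**Inputs from the protocol:** allocation by factory, 1:1; 8 or 4 factories; at least 80 workers per factory; level 0.05.

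**Assumptions:**

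- ICC of the change score from 0.001 to 0.05. The ICC of the change is the relevant one, because D-in-D on the same people removes stable differences between factories.
- 80 workers per factory for outcomes in all workers, such as knowledge and attitude.
- 40 per factory as an illustration for quit rate (smokers only) and cotinine (non-smokers only), since neither uses the whole factory.

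**Formulas**, with m workers per factory:

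- Design effect: DE = 1 + (m − 1) × ICC
- True standard error divided by the one that ignores factory: √DE
- True type I error of a nominal 5% test that ignores factory: 2 × [1 − Φ(1.96/√DE)]

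Worked example, m = 80 and ICC = 0.01: DE = 1 + 79 × 0.01 = 1.79; √DE = 1.34; 1.96/1.34 = 1.46; type I error 14.3%.

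| m | ICC of change | DE | √DE | Type I error |
|---|---|---|---|---|
| 80 | 0.001 | 1.08 | 1.04 | 5.9% |
| 80 | 0.01 | 1.79 | 1.34 | 14.3% |
| 80 | 0.02 | 2.58 | 1.61 | 22.2% |
| 80 | 0.05 | 4.95 | 2.22 | 37.8% |
| 40 | 0.001 | 1.04 | 1.02 | 5.5% |
| 40 | 0.01 | 1.39 | 1.18 | 9.6% |
| 40 | 0.02 | 1.78 | 1.33 | 14.2% |
| 40 | 0.05 | 2.95 | 1.72 | 25.4% |

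The error reaches 10% at an ICC of about 0.005 with m = 80, and about 0.011 with m = 40.

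**Simulation check.** In 20,000 null trials per setting, with 80 per factory, a worker-level t-test on change scores rejected in 14.3% (ICC 0.01) and 37.9% (ICC 0.05) of trials with 8 factories, and in 14.3% and 38.9% with 4. At ICC 0 it rejected in about 5%. A t-test on factory mean changes rejected in 4.8% to 5.1% in every setting tried (4 or 8 factories, 40 or 80 workers, ICC 0, 0.01 or 0.05).

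**Effect of the factory count.** A factory-level test has (number of factories − 2) degrees of freedom:

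- 8 factories: 6 df, critical value 2.45. There are 70 ways to choose 4 of 8, so the smallest two-sided permutation p is 2/70 = 0.029.
- 4 factories: 2 df, critical value 4.30. There are 6 ways to choose 2 of 4, so the smallest two-sided permutation p is 2/6 = 0.33.

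With 4 factories no test based on the allocation alone can reach 0.05. A t-test could, but only by relying on normality of factory means that four factories cannot verify.

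**The case against.** The strongest objection is that the protocol never says its D-in-D treats workers as independent. D-in-D is a contrast; it can be run on factory means, in a mixed model or with cluster-robust errors. Such detail often sits in a SAP, and none is shown here. The protocol also plainly knows about clustering, since it calls factories clusters and plans to estimate an ICC. This stands in part: a reader might infer that an individual-level analysis is prescribed, and the text does not support that. But the Data analysis section does fix the level, the intention-to-treat principle, the imputation method, the D-in-D and the regression families. In a trial with 8 or 4 allocated units, the unit of inference is a design feature and belongs beside those choices.

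Three further limits stand in full:

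- A reader might take the logistic and linear regressions as tests of effectiveness. They are not: they explore associations within the intervention arm and contain no comparison of arms. Clustering affects their intervals, but not an effectiveness claim.
- A reader might conclude that the false-positive rate is far above 5% whatever the data. That depends on an ICC the protocol does not give; at 0.001 the error is only 5.5% to 5.9%.
- Effectiveness is secondary. Feasibility and acceptability are assessed by questionnaire in the intervention group and by interview, with no test between arms.

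**Conclusion.** The point holds in conditional form. The protocol sets a 0.05-level effectiveness analysis for a factory-allocated trial and states no allowance for factory in it. If factory is left out, intervals are too narrow for any positive ICC of the change. The excess is slight at an ICC near 0.001. From 0.01 to 0.05 it is substantial: about 14% to 38% at 80 workers per factory, and about 10% to 25% at 40. These figures rest on an assumed ICC, equal factory sizes and a two-sided test.

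The damage is confined to the secondary effectiveness outcomes, the intervals of the exploratory regressions and the precision attached to the effect size for the main trial. It does not undermine the pilot's primary aim, but it should be settled before any effectiveness result is reported.

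**What to change.** - **D-in-D.** State that each factory's mean change (or proportion, for quitting) is computed and the arms are compared with a t reference on (number of factories − 2) degrees of freedom. A mixed model with a factory effect and a small-sample degrees-of-freedom correction is an acceptable alternative. The two are not generally equivalent when factory sizes differ or the outcome is binary, so one should be named as the main analysis.
- **Regressions.** Label the intervention-arm regressions exploratory and acknowledge factory clustering in their intervals. With only 4 or 2 factories in that arm, a factory effect will be poorly estimated, and the report should say so.
- **Factory count.** Reconcile 8 and 4. With 8, use 6 df (critical value 2.45). With 4, make no significance claim and report estimates with cluster-based 95% intervals on 2 df (4.30), read as descriptive.

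The cost is a few sentences of protocol or SAP wording and a little analysis work, with no extra data. Intervals widen. With 8 factories of 80 workers, the half-width grows relative to an analysis ignoring factory by about √DE × 2.45/1.96: 1.34 × 1.25 ≈ 1.7 at an ICC of 0.01, and 2.22 × 1.25 ≈ 2.8 at 0.05. That is the precision the design actually has.
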